## 2.3 POPULATIONS FOR ANALYSES

*Participants will be included if they complete the experimental session, have saved data, and do not fall below 2.5 s.d. below the mean of accuracy performance for the group.*

## 2.4 STATISTICAL ANALYSES

### 2.4.1 GENERAL APPROACH

As a guide, the following should be addressed, as appropriate:

- Descriptive statistics:means with standard deviations.
- Inferential tests:  $p$ -value=.05

---

#### 2.4.2 ANALYSIS OF THE PRIMARY ENDPOINT(S)

For both Reaction time and Accuracy, we will perform an ANOVA with these factors: Cue Meaning (Target Color Positive Cue or Distractor Color Negative Cue) x Cue Meaning Repetition (Repeat, Non-Repeat) X Cue Color Repetition (Repeat, Non-Repeat) Repetition.

---

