## 2 INTRODUCTION

### 2.1 STUDY RATIONALE

The PI provided the first evidence that attentional control can also be used to ignore known distractor features (Arita, [name], & Woodman, 2012). In this study, participants received a cue before each trial of a visual search task where they searched for a shape-defined target (a gap-up or gap-down Landolt-c) and reported the location of the gap. The cue could be a positive cue (indicating the target would appear in that color in the upcoming array), a negative cue (indicating the target *would not* appear in that color in the upcoming array), or a neutral cue (the cued color did not appear in the upcoming array). These cue meanings were manipulated across blocks. Importantly, because only two colors appeared in the search array, the positive and negative cues had the same information value. If participants used the cue, they could reduce the number of items they needed to search to find the target by half. We found participants can use visual attentional control to actively ignore items based on a feature cue, as indicated by reaction time (RT) benefits for the negative cued condition compared to the neutral condition.

In this study, participants will receive a cue on each trial that indicates a feature (e.g. red) and the cue meaning (positive + or negative -). Across trials, we will be able to independently alter the feature template and the cue meaning (Figure 5A). This will allow us to ensure the results are driven by shifts in the cue meaning, and not simply alterations to the color that is cued. This will lead to trials where both the feature and the meaning repeat (RE-repeat trials), trials where only the cue feature changes (CC-color change, meaning repeat), trials where only the cue meaning changes but the color repeats (MC-meaning change, color repeat), and trials where both feature and cue meaning change (BC-both change). To look for task switching costs, we will subtract the reaction times for repeat trials from each type of switch trials. Importantly, the visual search is defined by a shape-defined target across all trials, meaning that there should be no cross talk or response interference that could interfere with our ability to measure task-switching costs (Koch, Poljac, Müller, & Kiesel, 2018).

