## 3 OBJECTIVES AND ENDPOINTS

OBJECTIVES	ENDPOINTS	JUSTIFICATION FOR ENDPOINTS	PUTATIVE MECHANISMS OF ACTION

Primary
 
Compare Task-Switching Costs for Positive Target Cues and Negative Distractor Cues
	Reaction Time Accuracy	Cognitive Function	Conflict in Cognitive Control leads to task-switching costs

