## 5.5 STRATEGIES FOR RECRUITMENT AND RETENTION

We plan to include women and minorities in this study. Participants will be recruited from the Lehigh University community. As such, we expect the ethnicity distribution of our sample to roughly match the ethnicity distribution of Lehigh (see Figure 1). Lehigh's student body is 55% male and 45% female, so we also expect this to be represented in our sample. We will gather information on participant age, sex, and ethnicity for reporting purposes, and these factors will be entered into analysis as covariates in our statistical analyses. We have no a priori expectations of differences based on these factors from prior research, but will include these factors in our analysis to ensure that previous research has not neglected between group differences.

**Rationale for selection:** Our research is designed to assess basic research related to human visual attentional control. As such, we assume the basic processes will be shared among most adults humans. We will take a convenience sample of adults to learn more about these basic procedures.

**Outreach programs:** Participants will be recruited from low-level Psychology participant pools, which are often taken as a general education requirement at Lehigh. Paid participants will be recruited via fliers and the Lehigh Paid Participant Pool. Fliers are posted around Lehigh's campus as well as in public locations within the community (grocery stores, other higher education institutions, coffee shops, etc.). Most paid participants come from the Lehigh community, so we expect the sampling to draw heavily from Lehigh.

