## 6 STUDY INTERVENTION(S) OR EXPERIMENTAL MANIPULATION(S)

## 6.1 STUDY INTERVENTION(S) OR EXPERIMENTAL MANIPULATION(S) ADMINISTRATION

### 6.1.1 STUDY INTERVENTION OR EXPERIMENTAL MANIPULATION DESCRIPTION

Participants will receive one of three types of visual cues before performing a visual search task. Positive cues for visual search (cues to enhance), or negative cues for visual search (cues to suppress). After subjects receive the color cue for a trial, they will perform a visual search task for a shape-defined target (landolt-C). We will examine task switching costs for changes in the color of the cue, changes in the meaning of the cue, neither or both. We will measure 'task-switching costs' by contrasting reaction times when an aspect of the trial changes compared to when neither aspect of the trial changes compared to the previous trials. We will collect behavioral results using Matlab and a computer.

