## 2 STATISTICAL CONSIDERATIONS

### 2.1 STATISTICAL HYPOTHESES

If the negative template requires the general inhibition of the oculomotor system to reduce the likelihood of the prepotent response, we expect to find a unidirectional switch cost (e.g. a switch cost for positive cues which is not present for negative cues).

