## 2.2 SAMPLE SIZE DETERMINATION

**GPower analysis: Repeated measures ANOVA with 8 factors (4 different trial types x 2 cue types, positive vs. negative cues)**

**F tests** - ANOVA: Repeated measures, within factors

**Analysis:** A priori: Compute required sample size

**Input:** Effect size f = 0.2

α err prob = 0.05

Power (1-β err prob) = 0.8

Number of groups = 1

Number of measurements = 8

Corr among rep measures = 0.5

Nonsphericity correction ε = 1

**Output:** Noncentrality parameter λ = 15.3600000

Critical F = 2.0668747

Numerator df = 7.0000000

Denominator df = 161

Total sample size = 24

Actual power = 0.8115711

We will recruit 24 participants to meet the required sample size.

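### The stated power of 0.81 belongs to a 7-df omnibus test that the planned 2x2x2 ANOVA does not contain, and the plan names no effect or endpoint that decides the switch-cost hypothesis

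*Combined protocol and SAP*

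**What the plan says.** - **Objective and endpoints** (3 Objectives and Endpoints): the primary objective is "Compare Task-Switching Costs for Positive Target Cues and Negative Distractor Cues". Reaction time and accuracy are listed together as its endpoints, neither ranked above the other.
- **Hypothesis** (Statistical Hypotheses): a unidirectional cost, explained as "a switch cost for positive cues which is not present for negative cues". The direction is given, but no F-test or contrast is attached to it.
- **Switch cost** (Study Rationale): "we will subtract the reaction times for repeat trials from each type of switch trials". The intervention description (6.1.1) likewise measures it "by contrasting reaction times when an aspect of the trial changes compared to when neither aspect of the trial changes". Both are in reaction time. The rationale says colour is varied to "ensure the results are driven by shifts in the cue meaning, and not simply alterations to the color that is cued".
- **Primary analysis** (2.4.2): "For both Reaction time and Accuracy, we will perform an ANOVA with these factors", followed by three two-level factors. General Approach gives a .05 level and no rule for combining endpoints or effects.
- **Sample size** (2.2): f = 0.2, alpha 0.05, 8 measurements, correlation 0.5, epsilon 1, giving "Numerator df = 7.0000000", 161 denominator df, 24 participants and power 0.8115711.
- **Further terms**: for age, sex and ethnicity, "these factors will be entered into analysis as covariates in our statistical analyses" (5.5). The sub-group section adds sex as a between-subjects variable.

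**The concern.** The sample size rests on a test that asks whether the eight cell means differ in any way at all. The hypothesis asks something narrower: whether the cost of changing cue meaning differs between positive and negative cues. In the planned ANOVA that is one interaction with 1 df. A power figure for the first question says little about the second, so a reader cannot tell from the plan how likely the study is to detect what it is about.

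Two further gaps affect what may be concluded. With no deciding effect or endpoint named, the choice can be made after the results are seen. The hypothesis also contains a claim of absence for negative cues, and the ANOVA does not test absence. A significant interaction also arises when both cue types carry a cost and the costs are unequal. A non-significant negative-cue cost may only reflect imprecision.

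**Working it through.** **Inputs.** From 2.2: f = 0.2, n = 24, m = 8 measurements, correlation 0.5, epsilon 1, alpha 0.05. From 2.4.2: three factors of two levels. Assumed, because the documents give no figure: the share of the effect lying in the interaction, the correlation between endpoints, and the correlation between the two cue-type costs. Below, dz is a mean within-person difference divided by the SD of that difference.

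**1. The plan's own figure.** lambda = f² x n x m / (1 - correlation) = 0.04 x 24 x 8 / 0.5 = 15.36. The df are 7 and 23 x 7 = 161. Critical F is 2.0669 and power is 0.8116. The stated figure reproduces exactly.

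**2. Is that test in the planned ANOVA?** A 2x2x2 within-subject ANOVA has seven effects (three main effects, three two-way interactions, one three-way), each with (2-1) products = 1 df. None has 7 df.

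**3. Power of Cue Meaning x Cue Meaning Repetition, F(1,23), critical F 4.279, n = 24.**

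| Share of the assumed effect in this interaction | lambda | Power |
|---|---|---|
| all | 15.36 | 0.96 |
| half | 7.68 | 0.76 |
| a third | 5.12 | 0.58 |
| a seventh | 2.19 | 0.29 |

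If f = 0.2 is re-entered for a two-level contrast (m = 2), lambda = 0.04 x 24 x 2 / 0.5 = 3.84 and power is 0.47. Without assuming a share: 80% power needs lambda 8.56, so dz = √(8.56/24) = 0.60.

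**4. False-claim rate if either endpoint could decide**, one interaction per endpoint, no true cue-type difference, two-sided .05 tests:

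- Predicted direction only: 1 - 0.975² = 4.9% with independent endpoints. By simulation, 4.5% at endpoint correlation 0.5 and 3.9% at 0.8.
- Either direction: 1 - 0.95² = 9.75% with independent endpoints. By simulation, 9.0% at 0.5 and 7.9% at 0.8.

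**5. What a non-significant negative-cue cost shows** (paired t-test, n = 24, 23 df). A real cost is non-significant with probability 0.71 at dz 0.3, 0.53 at dz 0.4 and 0.35 at dz 0.5. The 95% confidence interval has a half-width of 0.42 SD.

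**6. Price of requiring the positive-cue cost as well as the interaction.** Assume a true cost for positive cues only, interaction dz 0.60 and equal SDs of the two costs. The interaction alone then has power of about 0.80. By simulation, the joint rule has power of about 0.80, 0.69, 0.51 and 0.38 at correlations of 0, 0.5, 0.7 and 0.8 between the two cue-type costs.

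**The case against.** The best defence is that the plan can be pieced together. Both definitions of switch cost are in reaction time, colour is plainly a control, and the hypothesis states its direction. A sympathetic reader arrives at the reaction-time interaction, tested at .05. Much of this stands, and it rules out several stronger readings:

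- **That the plan carries an 8-10% false-positive risk.** That needs two things the plan does not state: that either endpoint suffices, and that a result in the opposite direction would count. An opposite result would contradict the hypothesis. Claims in the predicted direction from either endpoint stay at about 4-5% without adjustment.
- **That 24 participants are too few.** The arithmetic in 2.2 is correct, and the interaction's power could be well above or well below 0.80. The synopsis also gives 27 participants; at n = 27 the half-share power is 0.81 rather than 0.76.
- **That switch cost is defined in two contradictory ways.** The rationale subtracts full-repeat trials from each switch type. The ANOVA's meaning-repetition effect averages the meaning change over colour repeated and colour changed. These can differ, but both come from the same eight cell means and both can be reported. Which one leads is a matter of preference.

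The defence does not reach the power statement, which belongs to no planned test on any reading. It also does not remove the endpoint ambiguity, because the objectives table and 2.4.2 give accuracy equal standing. And it does not answer the point about absence.

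**Conclusion.** The point holds in this limited form. That the 0.81 is not the power of any effect in the planned ANOVA follows from the factor levels alone and needs no assumption. The power of the relevant interaction is unstated: 0.29 to 0.96 at n = 24 over the assumed shares, with 0.47 on the two-level reading. It reaches 80% only if the true dz is about 0.60. Whether the sample is adequate cannot be settled from the documents.

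The missing deciding effect and endpoint is a gap in specification rather than a demonstrated inflation of error. The 8-10% applies only to a claim of some cue-type difference, in either direction and from either endpoint, at assumed endpoint correlations of 0 to 0.8.

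The claim of no cost for negative cues cannot be supported by the planned tests alone. The 53% figure assumes a true dz of 0.4 and n = 24. These points should be corrected; none makes the study unworkable.

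**What to change.** 1. **In 2.2**, say that 0.81 is the power of the 7-df omnibus test. Add the power of the 1-df interaction with its assumed effect, or the detectable effect: dz of about 0.60 for 80% power at n = 24.
2. **In 2.4.2**, name Cue Meaning x Cue Meaning Repetition on reaction time as the single primary test, two-sided .05. Make accuracy secondary, as a check on speed-accuracy trade-off. Label the other ANOVA effects and the sex, age and ethnicity terms exploratory.
3. **Also in 2.4.2**, claim a unidirectional cost only if the interaction is significant in the predicted direction and the positive-cue cost is significant. Report the negative-cue cost with a 95% confidence interval, and do not call it absent because it is non-significant.

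**Cost.** This is wording only and needs no new data. Accuracy can no longer support a primary claim by itself, and the restated power may fall below 0.80. The joint rule in step 3 may also cost power: at an interaction of dz 0.60 there is almost no loss if the two cue-type costs are uncorrelated, but a large one if they are strongly correlated (last step of the working). The team should state the correlation it expects before adopting the rule.

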#### 2.4.3 SAFETY ANALYSES

N/A

---

#### 2.4.4 BASELINE DESCRIPTIVE STATISTICS

N/A

---

#### 2.4.5 PLANNED INTERIM ANALYSES

N/A

---

#### 2.4.6 SUB-GROUP ANALYSES

We will include sex as a between-subjects variable in our analysis.

---

#### 2.4.7 TABULATION OF INDIVIDUAL PARTICIPANT DATA

N/A

---

#### 2.4.8 EXPLORATORY ANALYSES

N/A

---

### 3 SUPPORTING DOCUMENTATION AND OPERATIONAL CONSIDERATIONS

---

#### 3.1 REGULATORY, ETHICAL, AND STUDY OVERSIGHT CONSIDERATIONS

### 3.1.1 INFORMED CONSENT PROCESS

*Informed consent will occur before the study session begins.*

#### 3.1.1.1 CONSENT/ASSENT AND OTHER INFORMATIONAL DOCUMENTS PROVIDED TO PARTICIPANTS

Consent forms describing in detail the study intervention, study procedures, and risks will be given to the participant and written documentation of informed consent will be completed prior to starting the study intervention.

*Behavioral Research on Human Cognition: Lehigh IRB 864576-10*

#### 3.1.1.2 CONSENT PROCEDURES AND DOCUMENTATION

*Participants are told:* Ok, the next thing I will have you do is fill out the informed consent document. The important things to note about the consent document are that:

- >Your participation is voluntary
- >If you choose to withdraw your participation, you will still be given your experimental credit
- >Your name will not be associated with your data
- >Your name will be kept confidential

#### 3.1.2 STUDY DISCONTINUATION AND CLOSURE

This study may be temporarily suspended or prematurely terminated if there is sufficient reasonable cause. Written notification, documenting the reason for study suspension or termination, will be provided by the suspending or terminating party to NEI. If the study is prematurely terminated or suspended, the Principal Investigator (PI) will promptly inform the Institutional Review Board (IRB), and sponsor/funding agency and will provide the reason(s) for the termination or suspension.

### 3.1.3 CONFIDENTIALITY AND PRIVACY

We will collect behavioral results using Matlab and a computer. All data will be recorded using a non-identifiable participant code (e.g. TS\_B01) to ensure participant confidentiality. All informed consent documents will be kept in a lockable cabinet in a locked room.

Participant confidentiality and privacy is strictly held in trust by the participating investigators, their staff, and the sponsor(s) and funding agency. This confidentiality is extended to the data being collected as part of this study. Data that could be used to identify a specific study participant will be held in strict confidence within the research team. No personally-identifiable information from the study will be released to any unauthorized third party without prior written approval of the sponsor/funding agency.

All research activities will be conducted in as private a setting as possible.

The study monitor, other authorized representatives of the sponsor or funding agency, representatives of the Institutional Review Board (IRB), regulatory agencies or representatives from companies or organizations supplying the product, may inspect all documents and records required to be maintained by the investigator.

The study participant's contact information will be securely stored at each clinical site for internal use during the study. At the end of the study, all records will continue to be kept in a secure location for as long a period as dictated by the reviewing IRB, Institutional policies, or sponsor/funding agency requirements.

At the end of the study, all study databases will be archived at Open Science Framework.

#### Measures Taken to Ensure Confidentiality of Data Shared per the NIH Data Sharing Policies

It is NIH policy that the results and accomplishments of the activities that it funds should be made available to the public (see <https://grants.nih.gov/policy/sharing.htm>). The PI will ensure all mechanisms used to share data will include proper plans and safeguards for the protection of privacy, confidentiality, and security for data dissemination and reuse (e.g., all data will be thoroughly de-identified and will not be traceable to a specific study participant). Plans for archiving and long-term preservation of the data will be implemented, as appropriate.

#### Certificate of Confidentiality

To further protect the privacy of study participants, the Secretary, Health and Human Services (HHS), has issued a Certificate of Confidentiality (CoC) to all researchers engaged in biomedical, behavioral, clinical or other human subjects research funded wholly or in part by the federal government. Recipients of NIH funding for human subjects research are required to protect identifiable research information from forced disclosure per the terms of the NIH Policy (see <https://humansubjects.nih.gov/coc/index>). As set forth in 45 CFR Part 75.303(a) and NIHGPS Chapter 8.3, recipients conducting NIH-supported research covered by this Policy are required to establish and maintain effective internal controls (e.g., policies and procedures) that provide reasonable assurance that the award is managed in compliance with Federal statutes, regulations, and the terms and conditions of award. It is the NIH policy that investigators and others who have access to research records will not disclose identifying information except when the participant consents or in certain instances when federal, state, or local law or regulation requires disclosure. NIH expects investigators to inform research participants of the protections and the limits to protections provided by a Certificate issued by this Policy.

---

#### 3.1.4 FUTURE USE OF STORED SPECIMENS AND DATA

Data collected for this study will be analyzed and stored at Lehigh University. After the study is completed, the de-identified, archived data will be transmitted to and stored on the Open Science

Framework, for use by other researchers including those outside of the study. Reuse of anonymized data will be outlined in the informed consent.

---

### 3.1.6 SAFETY OVERSIGHT

*Safety oversight will be maintained by the PI, in consultation with the researchers, and, if necessary, Lehigh's IRB.*

---

### 3.1.7 CLINICAL MONITORING

*The PI and senior personnel (e.g. Post-doc, graduate students) will be responsible for training researchers and ensuring adherence to research protocols.*

---

### 3.1.8 QUALITY ASSURANCE AND QUALITY CONTROL

Quality control (QC) procedures will be implemented as follows:

**Informed consent** --- Study staff will review the consenting process and consent documents. Feedback will be provided to the study team to ensure proper consenting procedures are followed.

**Source documents and the electronic data** --- Data will be initially captured on research computers (see **Section 10.1.9, Data Handling and Record Keeping**) and the anonymized data will ultimately be maintained on a secure Lehigh data storage system.

**Intervention Fidelity** — Consistent delivery of the study interventions will be monitored throughout the intervention phase of the study by providing scripts for our research personnel. see **Section 6.2.1, Interventionist Training and Tracking**.

**Protocol Deviations** – The study team will review protocol deviations on an ongoing basis and will implement corrective actions when the quantity or nature of deviations are deemed to be at a level of concern.

Should independent monitoring become necessary, the PI will provide direct access to all trial related sites, source data/documents, and reports for the purpose of monitoring and auditing by the sponsor/funding agency, and inspection by local and regulatory authorities.

---

### 3.1.9 DATA HANDLING AND RECORD KEEPING

*No text is to be entered in this section; rather it should be included under the relevant subheadings below.*

*Each participating site will maintain appropriate medical and research records for this trial, in compliance with ICH GCP and regulatory and institutional requirements for the protection of confidentiality of participants. As part of participating in a NIH-sponsored or NIH-affiliated study, each site will permit authorized representatives of the NIH, sponsor, and regulatory agencies to examine (and when permitted by applicable law, to copy) clinical records for the purposes of quality assurance reviews, audits, and evaluation of the study safety, progress, and data validity. Indicate who will have access to records.*

*The following subsections should include a description of the data handling and record keeping for the conduct of the trial.*

---

